1. BACKGROUND

The methodology and test fixtures for the proposed study are informed by those used in previous studies of the strength capabilities of children, described below.

Exertions with Hands and Feet

Brown, Buchanan, and Mandel (1973, 1974) conducted a study of strength capabilities of children ages 2 through 6 years. The intent was to develop standards for toys and products. Two custom devices were developed: a push-pull and pull-apart tester to quantify hand and grip strength for a range of postures. The push-pull tester included several attachments: small diameter knob, narrow lever covered with a rubber sleeve, pull chain connected to a lever, twister (small diameter knob) mounted on the top and front of a testing device, and a hand dynamometer. The pull-apart tester included two cylindrical, T-shaped handles. No adaptations were made in the test rig to account for child anthropometry. For the push-pull measures, the tester was secured to a table, approximately 20 inches from the floor, and child participants were encouraged to use innovation, creativity, and volition to achieve maximum performance, approximating a more normal play condition. For the pull-apart measures, the child participant held the instrumented cylinder parallel and approximately perpendicular to the shoulders at chest height, and pulled the handles apart, bilaterally, and with the left or right hand extended forward. In addition to verbal encouragement, the testers included several colored lights that illuminated proportional to force exerted to motivate the children. Sample size for this study was 50 children per age group.

Owings et al. (1977) conducted a study of the strength of U.S. children, ages 2 to 10 years, with the intention of informing product safety design. The study included 33 isometric exertion measures conducted on an instrumented reclining chair. Isolated joint strength was measured at wrist, elbow, shoulder, ankle, knee, hip, and trunk. Torque was quantified about the available degrees of freedom (*e.g.*, shoulder flexion, extension, adduction, abduction, medial and lateral rotation). The customized chair included a series of cantilevered beams to form an adjustable exoskeleton that articulated in at least one plane and aligned to the center of rotation for each joint. Anthropometric measures were taken to scale the chair to fit each child. Friction contact surfaces and Velcro straps were used to standardize body posture without causing discomfort. To elicit maximal voluntary effort, caregivers and research staff provided verbal encouragement and visual feedback via a graphical display. Criterion for an acceptable measurement was defined as an exertion sustained for 4-6 seconds that was reasonably repeatable in a test-re-test, and representative of real-world observations in child strength. Force values were extracted using a

moving average over 1 second during the 3 seconds of the exertion. Sample size for this study was approximately 20-30 children per age group.

Grip strength measurements and upper extremity joint strength of children ages 2 to 10 years were collected as part of a larger study (Owings et al., 1977). Isolated joint strength about the elbow joint was quantified through a range of angles from flexion through to full extension. These measures were conducted using the instrumented reclining chair and protocol described for the whole-body joint torques. Grip strength measures included: 2-pt, 3-pt, 5-pt pinch grips, lateral grip, and squeeze with different degrees of hand closure. Grip strength measures were scaled to hand dimensions and performed at a range of one-centimeter increments between 2 and 9 cm. A customized grip transducer with varying handle sets was developed for this study. Force exertions were quantified as a 2D vector, defined the direction, magnitude, location of the resultant force in terms of normal and shear components.

Norris and Wilson (1995) compiled CHILDATA, a design resource that accumulated available references on children to provide guidance to product design. Data on body dimensions, strength, motor abilities, skills related to specific products, and psychological data were compiled from the United States, United Kingdom, and the Netherlands. Strength measures included pushing forward, pushing downwards, pushing sideways, pulling, and lifting up against a range of handle configurations, in both vertical and horizontal orientations, and in standing and seated postures. Hand grip strength measures included hitting force with a fist, wrist twist, opening strength, squeeze grip, and varying pinches. Sample sizes were relatively small for all of the measures, typically fewer than 20 per age group.

The United Kingdom Department of Trade & Industry, Government Consumer Safety Research (2000) conducted a strength study for design safety. Anthropometric and strength measurements were recorded for 150 participants, ranging from 2 to 90 years of age (n=17 for children ages 2-5). Hand strength measures included finger push, pinch-pull, hand grip, wrist-twisting, opening strength, push and pull strength. Additional measures of whole-body strength were also captured (DTI, 2002). Measures included maximal push and pull strength, push with thumb or 2-or-more fingers, push with shoulder, maximal pull with different grips, wrist twisting and push-and-turn strength, pull on a can ring-pull, and press and lift with foot. Force targets were presented in a range of size configurations, orientations and locations, defined by participant anthropometry. Participants used their dominant hand and self-selected posture during exertions. Visual feedback was provided throughout the protocol.

Few studies have measured strength in children younger than 24 months. Reus et al. (2013) presented a pull-strength test based on a simulated play scenario for children 6 months to 36 months of age. Children were positioned in a chair with an Infant Muscle Strength (IMS) meter attached to a metal platform with a strength sensor. The chair was adjusted based on the children's anthropometric characteristics, so that their trunk, shoulders, and hips were fixed, and

their feet could not touch the floor. Children pulled on a stiff toy held by the researcher, who provided counter strength to evoke maximum pulling strength. In the context of that work, the team noted that no standardized strength-testing methods were available for younger children.

Because the literature review uncovered no systematic studies of exertions with hands and feet for children less than 24 months old, the methodology and test fixtures for the youngest children in the proposed study will be adapted from those used for older children, with consideration for child development patterns and capabilities.

Bite Strength

Within the CHILDATA resource, Norris & Wilson (1995) cite four studies that quantify maximum bite force. The studies differed in the size, shape, position and material of the device used to record maximum force. Krogman (1971) recorded bite force at the anterior (incisal) and posterior (molar) sites within the dental arch for children ages 3-6 years. Garner and Hotwal (1973) quantified incisive biting force (front teeth) for children ages 10-14 years. Vertical bite force was measured by Wu (1978) for children who ranged from 18 months to 36 months and 3-8 years. Bite force was also measured on an instrumented test of a feeding bottle for children ages 2-3 years (CEN 1992).

Lemos et al. (2006) investigated the correlation between chewing performance and maximal bite force in children ages 7-12 years. Bite force was measured with a pressurized rubber tube connected to a sensor element. The tube was placed bilaterally between the posterior maxillary and mandibular teeth. Child participants were instructed to bite the tube with maximum force for 3 repetitions, holding each exertion for 5 seconds.

Mountain et al. (2011) measured bite force in children ages 3-6 years to address a gap in the literature on primary dentition of young children. A total of 205 child participants were asked to bite down for 2-3 seconds on a single tooth force gauge placed between the 1st and 2nd primary molars and at the central incisors. A customized device was designed to accommodate a single-use parallel bite sensor prong. Results showed substantial variability both between and within participants, with an overall range of 12 to 350 N.

Maximal occlusal bite force for children in different dentition stages were recorded in a large-scale study (Owais et al. 2013). Children were stratified across the range of dentition stages and ages 3 to 18 years. Two hundred children were measured within each dentition stage. Bite force was quantified alternatively on the right and left side, positioned at the second primary or the first permanent molars region. A portable occlusal force gauge was used, consisting of a hydraulic pressure gauge and bite element encased in a vinyl material. Maximal bite forces differed significantly across the dentition stages, increasing with age. Age, gender and height were found to be significant predictors of bite force at the later stages of dentition.

Conflicting evidence persists in defining the relationship between bite force and sex, age, size and physical characteristics of children. The variability of bite force data is considerable, with numerous factors influencing these results. To address this debate, Singh, Sandhu, and Kashyap (2012) investigated the relationship between bite force and facial morphology, classified by malocclusion groups, for children ages 12 to 16 years. Bite force was measured at intercuspal position and anterior bite position. No significant differences were observed between the classes of malocclusion.

Recently, Verma et al. (2017) published a comprehensive overview of bite force transducers, covering both custom devices used in research and commercially available systems. Many of the systems have limited applicability to child bite force measurement, due to the relatively large sizes (many more than 10 mm thick).

With guidance from the literature, the research team for the proposed study plans to fabricate a bite dynamometer suitable for measurements with young children. The dynamometer should enable measurement of maximum and sustained incisal and buccal bite strength, will be capable of being sterilized, and will be covered with sterile, disposable, non-allergenic material before measurement of each participant.

2. DESCRIPTION OF SAMPLING METHOD TO BE USED

The research team at UMTRI will collect data from approximately 800 children for the study.

A convenience sampling method will be used. The population of interest is children ranging in age from 3 months (bite strength) or 6 months (exertions with hands and feet) through 5 years. Participants for older age group ranges will be recruited first, followed by younger participants later in the study. They will be recruited via their caregivers through the University of Michigan Engage site, Craigslist, and flyers placed at UMTRI. The participants will be screened via a phone conversation with the caregiver. Inclusion criteria will include: the targeted age group; lack of current illness or injury; age appropriate cognitive and motor development, as reported by the caregiver; and the caregiver's ability to understand written and spoken English (older children should also understand spoken English).

3. DESCRIPTION OF PROCEDURES FOR INFORMATION COLLECTION, INCLUDING STATISTICAL METHODOLOGY FOR STRATIFICATION AND SAMPLE SELECTION

The target number of participants per age group in the proposed study (50 children) is the same as that used in Brown, Buchanan, and Mandel (1973, 1974), and it is larger than the number used in Owings et al. (1977), U.K. Department of Trade & Industry, Government Consumer Safety Research (2000), Reus et al. (2013), and studies referenced in Norris and Wilson (1995). In

addition, the proposed study has narrow age bands, to allow more precision in assessing child strength by age.

The data gathered in this study will be used for a wide range of purposes, some foreseen and others that will arise in the future. Thus, as an exploratory research study, it is not possible, or sensible, to specify a necessary level of precision for any estimates of population distribution parameters. A calculation of sample size, using data from a previous strength study and a potential confidence bound, is shown below, assuming the sample size criteria were met.

Gajdosik (2005) published data on isometric elbow flexions and extensions, shoulder flexion, and knee flexion and extension from a sample of 45 children ages 2 through 4 years. In this dataset, the coefficient of variation (COV) within 1-year age bins averaged 0.42. The mean strength for the exercise with the largest mean (knee extension) was about 40 N. Using a COV of 0.4, the estimated standard deviation within an age cohort is 16 N. Estimation of mean strength with 95% confidence and \pm 2 N precision would require a minimum sample size of 246 children.

When the anticipated COV is high, large sample sizes are needed to obtain high-precision mean estimates. For the current work, this suggests sample sizes as large as is practicable. Because the existing data are so sparse, even samples of 25 or more per age cohort will represent a substantial improvement. However, larger samples will improve precision of population parameter estimates.

This study is not designed to be powered adequately for hypothesis testing. However, this is a controlled, randomized, well-designed study with pre-specified criteria of interest, to explore. The results and information gathered in this study, ideally, will provide a framework that future hypothesis-testing studies can follow.

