4. PROCEDURES

UMTRI will begin the initial data collection starting with older children, which is why the IRB-approved materials and instruments provided currently focus on the older age range. The full age range of the study is children 3 months to 5 years of age.

Appendix A provides an example of how the OMB Control Number will be displayed on materials provided to participants. All time calculations have been included in the burden estimates provided in Supporting Statement A.

1. At UMTRI, a research assistant will explain and demonstrate the procedures to the caregiver and child. Written consent will be obtained from the caregivers, who will remain with the children at all times. Researchers will obtain verbal assent from the children who are old enough to provide it. An example of the written consent is provided,

- called Research Study Consent. This consent form references the age range 18 to 71 months, and after the initial data collection, the form will be amended to include children who are 3 months and older.
- 2. Researchers will obtain several standard anthropometric measurements from each child, including body weight and erect standing height. For bite strength participants, researchers will record mouth breadth and maximum mandibular opening.

 Anthropometric measures will allow the data to be normed to the U.S. population using anthropometric data from NHANES (CDC).
- 3. Researchers will record the participant's body shape using a whole-body laser scanner (VITUS XXL) and a Microsoft Kinect sensor. The research team has used both of these systems in several previous child studies. The laser scanner captures a high-resolution image of the subject's body shape in about 12 seconds. The Kinect will be used to capture the force-exertion postures. The laser-scan data will be used to create a subject-specific avatar that is used to aid posture tracking with the Kinect. The posture data are valuable to characterize the tactics that the children use for each exertion.

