6. DESCRIBE ANY TESTS FOR PROCEDURES OR METHODS TO BE UNDERTAKEN

The Child Strength Study will be based on convenience sampling and is not intended to be a representative sample to accurately reflect the characteristics of the children living in the United States. The sampling technique and sample size for the proposed study is consistent with previous child strength studies. These data have been used to draw inferences about the strength capabilities of children in the United States. To address the limitations of convenience sampling and ensure the representativeness of the study, UMTRI will use statistical methods to relate the measures strength to child age, as well as anthropometric factors that vary with age, such as body weight and standing height. This will allow the data to be normed to the U.S. population using anthropometric data from NHANES (CDC).

Initial pilot testing has been conducted, and an additional pilot study will be conducted to refine the data collection procedures and instruments, followed by the full study. Because this pilot is designed solely to test the study methods and not for analysis of the data, researchers will select the pilot participants.

COVID-19 Mitigation

UMTRI researcher have developed a safety protocol to include COVID-related precautions. UMTRI researchers are required to adhere to guidance from the University of Michigan Office of Research concerning human subject testing. The Office of Research has issued guidance for human research during the pandemic, which is available on their website (https://research.umich.edu/covid-19/human-research-during-covid-19/); this guidance is updated regularly to address changing health and safety measures. As of December 2021, the University of Michigan requires research team members to wear a face covering when conducting face-to-face interactions with human research participants; University of Michigan faculty, staff, and students are required to receive the COVID-19 vaccination. The ability to conduct human subjects testing will be based on local conditions and applicable mandates. CPSC has reviewed the risk-mitigation protocols recommended by the Office of Research and implemented by UMTRI, and the Child Strength Study will proceed only on the basis that these mitigation protocols will be adhered to.

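### The population is defined by age alone and the results are to be normed to the U.S., but entry requires caregiver-reported age-appropriate development, a gap that norming on age and body size cannot close

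*Protocol*

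**What the plan says.** Section 2 sets the target by age: "The population of interest is children ranging in age from 3 months (bite strength) or 6 months (exertions with hands and feet) through 5 years". The same paragraph lists the entry criteria. Besides the targeted age group and language ability, they are "lack of current illness or injury" and "age appropriate cognitive and motor development, as reported by the caregiver". On how these are checked it says: "The participants will be screened via a phone conversation with the caregiver". No instrument or threshold for development is stated there.

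Section 4, item 2 says what the body measurements are for: "Anthropometric measures will allow the data to be normed to the U.S. population using anthropometric data from NHANES (CDC". Section 6 repeats this and names the variables: age, body weight and standing height. Developmental status is not among them.

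On representativeness, section 6 says two things in one paragraph. It first says that the study "is not intended to be a representative sample to accurately reflect the characteristics of the children living in the United States". It then says: "To address the limitations of convenience sampling and ensure the representativeness of the study, UMTRI will use statistical methods".

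**The concern.** The target, the entry rule and the claim do not describe the same children. The target is every child of a given age. The entry rule admits children judged to be developing typically. The claim is about the U.S. population.

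This matters because motor development for age plausibly goes with strength for age, which is what the study measures. If children who fail the criterion are weaker on average, the sample holds too few weak children in each age band. Someone who later reads a low percentile as a U.S. value would then have a figure that more children fall below than the label says. This bias does not shrink as more children are enrolled.

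The problem is separate from convenience sampling. A probability sample with the same entry rule and perfect norming on body size would have the same gap. Nor can later analysis repair it, because excluded children are never measured.

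**Working it through.** **Inputs from the protocol (section 3).** Mean 40 N for knee extension, the exercise with the largest mean in the cited isometric strength study; COV 0.4; hence SD 0.4 × 40 = 16 N within an age cohort; 50 children per age group.

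**The protocol's own figure.** n = (1.96 × 16 / 2)² = 15.68² = 245.9, rounded up to 246. This reproduces. It concerns the precision of a mean and is not affected by this point; it is used here only to confirm the scale.

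**Inputs not in the protocol (assumptions).** The share p excluded on development, taken as 1% to 10%, and the mean strength deficit d of excluded children, in SD units. Strength is taken as normal with SD 16 N in both groups.

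**Model 1: mixture.** Eligible children follow N(40, 16). Their 5th percentile is 40 − 1.645 × 16 = 13.68 N and their 95th is 66.32 N. The 5th percentile x of all children solves

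(1 − p) Φ((x − 40)/16) + p Φ((x − 40 + 16d)/16) = 0.05.

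The share of all children below 13.68 N is 0.05(1 − p) + p Φ(−1.645 + d). The mean is overstated by 16pd.

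| p | d | 5th percentile, all children (N) | 5th percentile too high by (N) | 95th percentile too high by (N) | Mean too high by (N) | Share of all children below 13.68 N |
|---|---|---|---|---|---|---|
| any | 0 | 13.68 | 0 | 0 | 0 | 5.0% |
| 1% | 1 | 13.36 | 0.32 | 0.07 | 0.16 | 5.2% |
| 5% | 1 | 12.10 | 1.58 | 0.37 | 0.80 | 6.0% |
| 10% | 1 | 10.62 | 3.06 | 0.75 | 1.60 | 7.1% |

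With d = 0.5 the error in the 5th percentile is 0.12, 0.58 and 1.13 N at p = 1%, 5% and 10%. With d = 2 it is about 5 N at 5% and about 10 N at 10%.

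**Model 2: selection on a correlated score.** Here all children follow N(40, 16), and the lowest 5% on a motor score with correlation ρ to strength are excluded. By simulation, the 5th percentile of admitted children exceeds that of all children by 0 N at ρ = 0, 0.8 N at ρ = 0.3, 1.7 N at ρ = 0.5, 2.9 N at ρ = 0.7 and 5.6 N at ρ = 1. Only ρ = 1 is a true cut-off of the weakest children.

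**Comparison with sampling error.** By simulation, with 50 children, the standard error of the 5th percentile is about 3.5 N when estimated from a fitted normal and about 4.3 N when taken from the ordered data.

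**What norming can do.** Norming on age, weight and height reweights or predicts from children who were measured. It recovers the population distribution only if, at a given age, weight and height, admitted and excluded children have the same strength distribution. The protocol gives no ground for that, and the entry rule makes it doubtful for hand and foot exertions.

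**The case against.** The strongest reply is that section 6 openly says the sample is not meant to be representative. That would settle the matter if the paragraph ended there. It goes on to say that statistical methods will secure representativeness, so the disclaimer is withdrawn where it is needed.

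Several other objections stand and limit the point:

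- A reader might infer that the weak end of the distribution is cut off and that low percentiles will certainly be too high. The documents do not support this. The criterion is a caregiver's report of development, not measured strength, so weak children with typical development still enter. The tail is thinned, and only if excluded children are weaker, which is plausible but not shown.
- Nothing in the protocol links bite force to motor development. Section 1 itself calls the evidence on what bite force depends on conflicting.
- The protocol names no low percentile as an output. It speaks of population distribution parameters in general, and its only worked example is a mean.
- Relative figures look large because the 5th percentile is small. At 10% excluded and a 1 SD deficit the overstatement is 13.68/10.62, about 29%, but that is 3 N. It becomes about 35% with a COV of 0.42, the average in the cited dataset, instead of the 0.4 used in the calculation. For a lenient phone criterion, 1% excluded is as defensible as 10%, and the overstatement is then about 2%.
- In one age band, sampling error of the 5th percentile may exceed the bias. The bias is nonetheless systematic.

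**Conclusion.** The mismatch is established from the text: an age-only population, an entry rule on development, and norming to the U.S. on variables that cannot recover the excluded children. The claim that representativeness is ensured therefore does not hold for this design.

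The numerical consequence is conditional. For hand and foot exertions, if excluded children are weaker on average, low percentiles are biased upward and high ones barely move. With normal strength, mean 40 N, SD 16 N and an assumed 1 SD deficit, the 5th percentile is about 0.3 N too high at 1% excluded and about 3 N at 10%. It is unbiased if development is unrelated to strength, and the error is larger if the deficit is larger. The documents give neither the share nor the deficit, so no single figure can be claimed, and none is claimed for bite force. The point should be corrected because it changes whom the results describe.

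**What to change.** Keep the entry criterion and make the claim match it.

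1. Section 2: define the population of interest as children of the stated ages who meet the eligibility criteria.
2. Section 4, item 2 and section 6: limit the claim to norming for U.S. age and body size among children who meet those criteria.
3. Section 6: remove the statement that this ensures representativeness.

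Optionally, at the existing phone screen, count exclusions for cognitive and for motor development separately by age group and report them descriptively. A share p from that tally should not be turned into a bound such as p + (1 − p)q on the U.S. percentile matching a reported percentile q. Callers are self-selected through a volunteer site, online advertisements and flyers, and caregivers of children with delays may never call, so p is not the U.S. share.

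The cost is wording in three places and, if chosen, one tally. No extra children or procedures are needed. The downside is a narrower claim about whom the results describe.

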- 4. In the laboratory, the children will perform a sequence of tasks to test maximal exertions with their hands and feet. For standing tasks, they will grip a padded handle with one or both hands, as instructed, and push or pull as hard as they can. Each exertion will be targeted for approximately 5 seconds, including the ramp-up and release. Feedback will be provided to the participants via a graphic display that shows their maximum level achieved, so that they can be encouraged to go beyond that level, if possible. For bite strength, children will bite on a bite dynamometer that is fabricated to suit the age cohort.
- 5. For some trials, the participant will be seated in a specially constructed laboratory chair. Seated exertions will include pushes and pulls with the hands and pushes with one and both feet. Conditions will be varied to avoid loading up one part of the body consecutively. For example, a hand pull might be followed by a hand or foot push. Researchers will determine the trials to be performed, based on the result of previous pilot testing and the ability of the child. For example, if researchers have already established that children 36 months and up can reliably perform standing two-hand pushes, they will choose different types of exertions with subsequent subjects.
- 6. Researchers will record video and still images of the trials. The video and images will be used by the research team to assess the children's performance, particularly their tactics for achieving the requested exertions. This information will be valuable for developing the measurement protocols.
- 7. Trials will be separated by a minimum of 15 seconds to allow time for recovery. Longer recovery time is anticipated to be impractical, due to a loss of attention from the child;

but switching between limbs and exertion directions will reduce fatigue. The caregivers will be engaged in every step of the process, including directing and encouraging the children.

- 8. The number of trials to be performed will depend on the capability and attention of the child, but the maximum duration of a child's participation in a single session will be 2 hours. A 5-minute break will be taken at least every 20 minutes, to allow the child to relax and play. The caregiver and child can take a break, or discontinue participation, at any time.
- 9. The caregiver will be paid an incentive of \$40 for up to 2 hours of participation.

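### The protocol calls the study controlled and randomized, but it describes no control and nothing that is randomised, and it gives no rule that balances the order of exertions

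*Protocol*

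**What the plan says.** Section 3, after stating that the study is not powered to test hypotheses, adds that "this is a controlled, randomized, well-designed study with pre-specified criteria of interest, to explore". It then offers the results as a framework for later hypothesis-testing work.

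On selection of children, section 2 states: "A convenience sampling method will be used". Section 6 repeats this: "The Child Strength Study will be based on convenience sampling and is not intended to be a representative sample". Section 2 also fixes the sequence of recruitment: "Participants for older age group ranges will be recruited first, followed by younger participants later in the study".

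On exertions, section 4, item 5, states: "Researchers will determine the trials to be performed, based on the result of previous pilot testing and the ability of the child". As an example, once researchers know that a given age range can do one task reliably, "they will choose different types of exertions with subsequent subjects". On order, the same item says: "Conditions will be varied to avoid loading up one part of the body consecutively".

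On recovery, item 7 states: "Trials will be separated by a minimum of 15 seconds to allow time for recovery". It explains that longer gaps would cost the child's attention and that changing limb and direction limits fatigue. Item 8 requires a break of 5 minutes no less often than every 20 minutes, caps a session at 2 hours, and lets the number of trials depend on how able and attentive the child is.

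**The concern.** A protocol that claims randomisation should say what is randomised and how. Here the claim appears once, as reassurance, and none of the procedures matches it. The data are intended for lasting archival use and for norming to national body-size data (sections 4 and 6). A later user who relies on the section 3 sentence could take a descriptive convenience sample for randomised evidence.

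There is also a practical side. The order of exertions within a child could be randomised at little cost, and the protocol itself expects attention to fade and recovery to be short. If some exertions tend to fall later in a session than others, their recorded values could partly reflect position rather than strength. If that tendency differed with age, it could enter the relation of strength to age that section 6 sets out to estimate.

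**Working it through.** **Step 1: the plan's own figure.** The only sample size calculated in the document is 246 (section 3). Inputs: mean about 40 N, coefficient of variation 0.4, precision ±2 N, 95% confidence.

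- SD = 0.4 × 40 = 16 N
- n = (1.960 × 16 / 2)² = 15.68² = 245.9, rounded up to 246

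The figure is reproduced; a t-based version gives 249. This is a one-sample precision formula with no comparator and no allocation ratio. Removing the words controlled and randomized therefore leaves it unchanged.

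**Step 2: where a control or a random element could lie.**

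- *Selection of children:* convenience sampling, stated in sections 2 and 6, with caregivers recruited through a university site, an online listing and flyers. Not random.
- *Sequence of recruitment:* older children before younger (section 2). Not random.
- *Groups:* age bands only. A child's age band is not assigned, and no comparator or control group appears in any section.
- *Which exertions a child performs:* decided by researchers from pilot results and the child's ability (section 4, item 5). This is assignment by judgement.
- *Number of exertions:* depends on the child (section 4, item 8). Not random.
- *Order of exertions:* varied to avoid loading one body part consecutively (section 4, item 5). No random or counterbalanced sequence is stated, and no one is named as choosing the order.

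None of the six supplies a control or a random element.

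**Step 3: whether the fatigue measures balance position.** Limb switching, the minimum gap and the breaks all act on recovery from recent effort. Balance is a different property: across children, each exertion type should fall early and late equally often. None of the measures ensures that.

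The timing leaves room for position to vary. An exertion of about 5 s plus the minimum 15 s gap makes a 20 s cycle, and 20 minutes is 1,200 s. Up to 1,200 / 20 = 60 exertions could therefore fit before a break falls due. This is a ceiling from the stated timings and not an expected count, which the protocol does not give.

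**Step 4: whether the effect can be sized.** Under a simple linear decline, the distortion between two exertion types would be the loss per trial position multiplied by the mean difference in position. The document gives neither quantity, and a linear model would also ignore recovery during breaks. No figure can be derived.

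**The case against.** The strongest defence has four parts.

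First, controlled may loosely mean laboratory conditions, and randomized may refer to an exertion order set out in an operational document that is not shown. The first reading is possible. The second cannot be excluded, but the protocol states the property and its own procedures do not show it. If such a scheme exists, the remedy is to state it.

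Second, a reader might infer that testers choose the order, and that fatigue is therefore confounded with exertion type as a matter of fact. The text does not say so. Researchers determine which trials are done; on order, it says only that conditions are varied. Confounding with position is possible but not shown, and bias in the age trend is one step further removed. This part of the defence stands.

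Third, the protocol takes real steps against fatigue: limb and direction switching, breaks at set intervals, and further breaks or withdrawal at any time. Two hours is a cap on participation and not a period of continuous effort. This also stands, within the limit shown in step 3 of the working.

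Fourth, the study is openly exploratory and says that its sample is not meant to be representative, so the label may mislead few careful readers. That lowers the stakes but does not make the sentence true.

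**Conclusion.** The sentence in section 3 is wrong as written. The protocol describes no control and no random selection, allocation, task assignment or order. This rests on the text alone and needs no assumption.

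The second part is conditional. Because no balanced order is stated, exertion type may be partly confounded with session position and attention, despite the measures against fatigue.

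It is tempting to attach a size. Assuming a loss of 0.5–1% per trial and a mean gap of 10–20 positions gives 5–20%. That could be set beside the 95% half-width at 50 children, 2.0096 × 0.40 / √50 = 11.4% of the mean. The half-width follows from the plan's figures, but both inputs to the 5–20% would be invented, and the product allows no recovery. The documents do not support a claim that order effects match or exceed sampling error.

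Correcting the label alters no sample size or estimate. Its importance lies in how the archived data will be described and used.

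**What to change.** Do one of the following before main data collection.

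1. In section 3, replace the words controlled, randomized with a description of an exploratory, descriptive study using convenience sampling.
2. Make a random element true and name it. In section 4, item 5, keep the choice of exertions as it is, but put each child's chosen exertions in a pre-generated random sequence, constrained so that one body part is not loaded consecutively. Record each trial's position so that order effects can be checked. Section 3 should then say that only the order of exertions within a child is randomised, and should drop the word controlled or explain it as laboratory conditions.

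The first option costs one sentence. The second adds a generated list and one recorded variable, and it keeps the existing rule on consecutive loading. Its downside is less freedom for testers to improvise, so documented deviations should be allowed when a child refuses. How position enters any model can be left to the analysis plan, but position has to be recorded at the time, because it may be hard to recover afterwards.
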